### 9.2.7 Medical Photography (cutaneous lesions)

If applicable, medical photography should be obtained. The collection time points follow the same schedule as imaging and may be performed more often if clinically indicated. Collection timepoints specified in the SoA are based on calendar days and are not adjusted for delays in treatment cycle start dates. Imaging and/or medical photography continues to be captured until disease progression or discontinuation (end of treatment [EoT]). The Site Imaging Manual (SIM) provides guidance in obtaining and submitting medical photography to the central imaging vendor.

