Pembrolizumab Administration				X		X		X	X				
C2D1: Minimum 8-hour observation period following completion of pembrolizumab infusion
	
New Anticancer Therapy Status											X	X		

Trial Phase:	Screening	Treatment (Treatment Cycle = 21 days)							End of Treatment (EoT)	Post-treatment		Notes	
		MK-7162 Mono-therapy		MK-7162 and Pembrolizumab Combination Therapy						Last Dose / Discontinuation	Safety Follow-up		
Visit or Cycle (C):		C1		C2		C3		C4	C5 thru C36	30 days after the last dose	Every 12 weeks after the last dose		
Scheduling Day (D):		D1	D15	D1	D15	D1	D15	D1	D1				
Schedule Window (Days):	-28 to -1		± 3	± 3	± 3	± 3	± 5	± 3	± 3	± 7	± 7	± 14	
Survival Status		← ----- →									X	Treatment and Safety Follow-up Phase: Upon Sponsor request, participants may be contacted for survival status at any time during the course of the study Survival Follow-up Phase: After Investigator determined PD or start of new anticancer treatment.	
Efficacy Procedures													
Tumor Imaging: RECIST 1.1 and iRECIST Response Assessment	X							X	X	X			
 
• Imaging obtained via CT, PET/CT, or MRI.
 
• Medical Photography for cutaneous lesions: Obtained on the same schedule as imaging
 
• On-treatment visit window: ± 7 days
 
 Screening Visit: Baseline tumor imaging and/or medical photography for cutaneous lesions should be performed within 28 days prior to first dose of MK-7162. Treatment Phase: Obtain first on-treatment imaging at Week 9 (C4D1); Obtain subsequent imaging every 9 weeks thereafter.
Medical Photography (cutaneous lesions)	X							X	X	X			
Safety Assessments and Procedures													
AE/SAE Review	X	X ← ----- → X							X	X			
Full Physical Examination	X								X	X			
Directed Physical Examination		X		X		X		X	X				

Trial Phase:	Screening	Treatment (Treatment Cycle = 21 days)								End of Treatment (EoT)	Post-treatment			
		MK-7162 Mono-therapy		MK-7162 and Pembrolizumab Combination Therapy							Last Dose / Discontinuation	Safety Follow-up	Survival Follow-up	
		C1		C2		C3		C4	C5 thru C36		30 days after the last dose	Every 12 weeks after the last dose		
Scheduling Day (D):		D1	D15	D1	D15	D1	D15	D1	D1					Notes
Schedule Window (Days):	-28 to -1			± 3	± 3	± 3	± 5	± 3	± 3	± 7	± 7	± 14		
Height	X													
Weight	X	X		X		X		X	X	X				

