Participants may receive study medication for up to 36 cycles. Participants will be treated until progressive disease, unacceptable toxicity, intercurrent illness that prevents further administration of treatment, Investigator's decision to withdraw treatment, participant withdrawal of consent, pregnancy of the participant, noncompliance with study medication or procedure requirements, participant completes treatment, or administrative reasons requiring cessation of treatment, at which point they will be discontinued from the study.

All participants will be followed for at least 30 days after their last dose of MK-7162 for AE monitoring. Serious adverse events will be collected for 90 days after discontinuation, 30 days if the participant initiates new anticancer therapy less than 30 days after study treatment discontinuation, or the day new anticancer therapy is initiated if between 30 days and 90 days after study treatment discontinuation. Participants with an ongoing AE of Grade  $> 1$  at the time of treatment discontinuation will be followed until resolution of the AE to Grade 0-1, until considered stable by the treating physician, or until beginning a new anticancer therapy, whichever occurs first.

Participants who discontinue treatment for reasons other than confirmed progressive disease will have post-treatment follow-up for disease status (including imaging) until disease progression, initiating a new anticancer therapy, withdrawing consent for study participation, or becoming lost to follow-up.

After confirmed disease progression, each participant who discontinues treatment will be contacted by telephone every 12 weeks ( $\pm 14$  days) for survival until withdrawal of consent to participate in the study, becoming lost to follow-up, death, or end of the study, whichever occurs first.

Specific procedures to be performed during the trial, as well as their prescribed times and associated visit windows, are outlined in the Trial SoA - Section 2. Details of each procedure are provided in Section 9 – Study Assessments and Procedures.

This trial will use an adaptive design based on prespecified criteria. Interim analyses will be conducted to examine clinical trial data on a continuous basis to allow for dose-finding decisions, safety, tolerability, and efficacy analysis.

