#### **9.2.4 End of Treatment and Follow-up Tumor Imaging**

For participants who discontinue study treatment, tumor imaging should be performed at the time of treatment discontinuation ( $\pm 4$  week window). If previous imaging was obtained within 4 weeks prior to the date of discontinuation, then imaging at treatment discontinuation is not mandatory. For participants who discontinue study treatment due to documented disease progression, this is the final required tumor imaging if the Investigator elects not to implement iRECIST.

For participants who discontinue study treatment without documented disease progression, every effort should be made to continue monitoring disease status by tumor imaging using the same imaging schedule used while on treatment (every 9 weeks) until the start of a new anticancer treatment, disease progression, death, withdrawal of consent, or the end of the study, whichever occurs first. Such imaging should be submitted to the central imaging vendor.

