#### **9.2.6 iRECIST 1.1 Assessment of Disease**

iRECIST is based on RECIST 1.1, but adapted to account for the unique tumor response seen with immunotherapeutic drugs. iRECIST will be used by the Investigator to assess tumor response and progression and to make treatment decisions. When clinically stable, participants should not be discontinued until progression is confirmed by the Investigator, working with local radiology, according to the rules outlined in Appendix 7. This allowance to continue treatment despite initial radiologic progressive disease (PD) takes into account the observation that some participants can have a transient tumor flare in the first few months after the start of immunotherapy, and then experience subsequent disease response. This data will be captured in the clinical database.

Clinical stability is defined as the following:

- Absence of symptoms and signs indicating clinically significant progression of disease
- No decline in ECOG performance status
- No requirements for intensified management, including increased analgesia, radiation, or other palliative care

Any participant deemed **clinically unstable** should be discontinued from study treatment at site-assessed first radiologic evidence of PD and is not required to have repeat tumor imaging for confirmation of PD by iRECIST.

If the Investigator decides to continue treatment, the participant may continue to receive study treatment and the tumor assessment should be repeated later to confirm PD by iRECIST, per Investigator assessment. Images should continue to be sent in to the central imaging vendor for potential retrospective BICR.

If repeat imaging does not confirm PD per iRECIST, as assessed by the Investigator, and the participant continues to be clinically stable, study treatment may continue and follow the regular imaging schedule. If PD is confirmed, participants will be discontinued from study treatment.

If a participant has confirmed radiographic progression (iCPD) as defined in Appendix 8, study treatment should be discontinued; however, if the participant is achieving a clinically meaningful benefit, an exception to continue study treatment may be considered following consultation with the Sponsor. In this case, if study treatment is continued, tumor imaging should continue to be performed following the intervals as outlined in Section 2 and submitted to the central imaging vendor.

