### **9.10.3.2 Survival Follow-up Visits**

Participants, who experience confirmed disease progression or start a new anticancer therapy will move into the Survival Follow-Up Phase and should be contacted by telephone every 12 weeks to assess for survival status until death, withdrawal of consent, or the end of the study, whichever occurs first.

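### The Schedule of Activities and Section 9.2.7 stop imaging at end of treatment while Sections 9.2.3, 9.2.4 and 5.1.1 continue it, and the survival follow-up trigger is stated in three different ways

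*Combined protocol and SAP*

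**What the plan says.** **Imaging after treatment stops.** Section 9.2.7 deals with cutaneous photography, but its sentence also covers imaging: "Imaging and/or medical photography continues to be captured until disease progression or discontinuation (end of treatment [EoT". The SoA imaging row (Section 2.1) is marked at Screening, Cycle 4, Cycles 5 to 36 and end of treatment. Both post-treatment columns are blank, and the treatment-phase note gives only an on-treatment schedule: "Obtain first on-treatment imaging at Week 9 (C4D1); Obtain subsequent imaging every 9 weeks thereafter".

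For participants who stop without documented progression, Section 9.2.4 says "every effort should be made to continue monitoring disease status by tumor imaging using the same imaging schedule used while on treatment". That interval is 9 weeks, and the follow-up ends at new anticancer treatment, progression, death, withdrawal of consent or study end. Section 5.1.1 also provides disease-status follow-up with imaging for anyone who stops for a reason other than confirmed progression. Section 9.2.3 lists the events that end imaging, and end of treatment is not one of them.

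**Survival calls.** Section 5.1.1 begins 12-weekly calls after confirmed progression. Section 9.10.3.2 says "Participants, who experience confirmed disease progression or start a new anticancer therapy will move into the Survival Follow-Up Phase". The SoA note on the survival phase says "After Investigator determined PD or start of new anticancer treatment", with no need for confirmation. Under Section 9.2.6 a clinically unstable participant is taken off treatment at first radiologic progression and "is not required to have repeat tumor imaging for confirmation of PD by iRECIST".

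**Study status.** The list of treatment-stopping reasons in Section 5.1.1 closes with "administrative reasons requiring cessation of treatment, at which point they will be discontinued from the study". Section 8.1 states that stopping treatment is not withdrawal from the study.

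**The concern.** Two groups could lose follow-up, depending on which text a site applies.

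- **Stopped without progression**, for example for toxicity or after 36 cycles. If the SoA and 9.2.7 are followed, their PFS assessment ends with the end-of-treatment scan. Stopping for toxicity may be related to prognosis, so this loss could be informative.
- **Stopped as clinically unstable at first radiologic progression**, with no confirmatory scan and no new therapy. If 5.1.1 or 9.10.3.2 is followed, nothing starts their survival calls. These participants are unwell, and inclusion criterion 1 requires that they have received, or been intolerant to or ineligible for, all treatment known to help. Losing them from OS is plausibly informative too.

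**Working it through.** The plan gives no figure to reproduce on this point, so the check sets the passages side by side.

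**1. When does imaging end?**

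| Source | Imaging after end of treatment, no progression |
|---|---|
| SoA imaging row | None marked |
| 9.2.7 | Ends at progression or end of treatment |
| 9.2.3 | Continues; end of treatment is not a stopping event |
| 9.2.4 | Continues every 9 weeks |
| 5.1.1 | Continues until progression, new therapy, withdrawal of consent or loss to follow-up |

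The first two rows cannot be followed together with the last three.

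**2. Which text would a site reach?** For participants who have stopped treatment, Section 8.1 points to the SoA and to Section 9.11.3. No Section 9.11.3 exists. The section with that title is 9.10.3, which points back to the SoA for visit requirements. Neither 8.1 nor 9.10.3 names 9.2.4. Section 9 also makes adherence to the SoA mandatory. Reading only the SoA is therefore a realistic path.

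**3. What would be lost per participant?** At 9-week spacing, 52 / 9 = about 5.8 scans per year for as long as the participant remains alive, progression-free and off new therapy.

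**4. Who receives survival calls?** Each trigger applied to participants who are off treatment:

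| Situation | 5.1.1 | 9.10.3.2 | SoA note |
|---|---|---|---|
| Confirmed progression | Yes | Yes | Yes |
| New therapy, no progression | Not stated | Yes | Yes |
| First progression, clinically unstable, no confirmatory scan, no new therapy | No | No | Yes |
| No progression, no new therapy | No | No | No |

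The third row is the gap, and it exists only where the 5.1.1 or 9.10.3.2 wording prevails over the SoA note. In the fourth row no text schedules survival calls. Apart from adverse event follow-up, regular contact rests on the 9-weekly imaging, so the imaging conflict matters for those participants.

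**5. What does the third-row group actually lose?** Not the RECIST 1.1 PFS event: 9.2.5 makes RECIST 1.1 the primary measure for the progression date, and that date is already recorded. The possible losses are scheduled OS calls and iRECIST confirmation. Section 5.1.1 might still give them imaging, because they stopped for something other than confirmed progression. However, that follow-up runs until disease progression, and the text does not say whether unconfirmed progression ends it.

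**6. Do other provisions close the gap?** Section 9.10.4 lets the Sponsor request survival status for participants with no scheduled contact, but this is on request and has no fixed timing. Section 5.1.1 collects serious adverse events for up to 90 days. Under 9.3.5, progression of the cancer under study is not reportable, so safety reporting cannot be relied on to record deaths from progression.

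**The case against.** The strongest reply is that the protocol already has the right rules. Section 9.2.4 is the dedicated section and is explicit, 5.1.1 and 9.2.3 agree with it, 8.1 keeps participants in the study, 9.1.9 encourages attendance at remaining visits, and the 9.2.7 sentence sits in a photography section. This stands to the extent that follow-up is planned. It does not remove the conflict with the SoA, which is where 8.1 and 9.10.3 send the reader.

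A reader might infer several stronger points that the documents do not support:

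- **That survival calls start only after confirmed progression.** New therapy is also a trigger in 9.10.3.2, 9.1.5.2 and the SoA, and the SoA needs no confirmation.
- **That participants who stop without progression have no planned PFS follow-up, or no contact after Day 30.** Sections 9.2.4 and 5.1.1 schedule imaging, and 5.1.1 follows ongoing adverse events above Grade 1 and collects serious events for up to 90 days.
- **That ORR, a secondary endpoint, is biased downward.** A response first seen at end of treatment would go unconfirmed only if the SoA and 9.2.7 are followed over 9.2.3, which calls for the confirmatory scan at least 4 weeks later, and over 9.2.4.
- **That PFS will be censored at discontinuation.** PFS and OS methods are deferred to the supplemental SAP, which is not among these documents.
- **That a count of affected participants can be given.** The documents contain no rate for either group. The two groups also lose different things, so they should not be added together.

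**Conclusion.** The plan contradicts itself on imaging after end of treatment and on what starts survival follow-up. Both contradictions should be corrected.

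The consequence is limited. It is mainly possible informative loss of PFS data in participants who stop without progression, and of OS data in those who stop at unconfirmed progression without new therapy. Both endpoints are exploratory. The loss arises only where a site follows the SoA and 9.2.7 on imaging, or 5.1.1 and 9.10.3.2 on survival calls. About 40 participants are planned for Part A, but the number on either path is unknown. Section 9.10.4 covers the OS gap only in part.

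**What to change.** 1. **SoA:** add a disease follow-up column that mirrors 9.2.4, with imaging or photography every 9 weeks until new anticancer treatment, progression, death, withdrawal of consent or end of study. Keep end of study in the list, because Amendment -02 was written to allow closure.
2. **Section 9.2.7:** replace the end-of-treatment stop with the stopping events of 9.2.3 and 9.2.4.
3. **SoA note, 5.1.1 and 9.10.3.2:** use one survival trigger, namely participants who have discontinued study treatment and have Investigator-determined progression (confirmed or not), or who start new anticancer therapy. The off-treatment condition is needed. Section 9.10.3.2 has no such qualifier, so simply replacing confirmed with Investigator-determined progression there would move clinically stable participants with unconfirmed progression, who may still be on treatment under Table 7, into survival follow-up.
4. **Section 5.1.1:** reconcile the sentence that discontinues participants from the study with 8.1. Correct the 8.1 references to Section 9.11.3 at the same time.

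The cost is amendment wording, one SoA column and a few more 12-weekly calls. No scans are added beyond those in 9.2.4. If few participants remain in follow-up, the supplemental SAP or clinical study report should at least state which follow-up rule was applied and how PFS and OS were censored.

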### 9.2.8 Eastern Cooperative Oncology Group (ECOG) Performance Scale

The investigator or qualified designee will assess ECOG status at screening, prior to the administration of each dose of trial treatment, and during the follow-up period as specified in Section 2 - SoA. Additional ECOG assessments may be performed as clinically indicated.

### 9.3 Adverse Events, Serious Adverse Events and Other Reportable Safety Events

The definitions of an adverse event (AE) or serious adverse event (SAE), as well as the method of recording, evaluating, and assessing causality of AE and SAE and the procedures for completing and transmitting AE, SAE and other reportable safety event reports can be found in Appendix 4.

Progression of the cancer under study is not considered an adverse event as described in Section 9.3.5 – Disease-Related Events and/or Disease-Related Outcomes Not Qualifying as AEs or SAEs, and Appendix 4.

AE, SAEs, and other reportable safety events will be reported by the participant (or, when appropriate, by a caregiver, surrogate, or the participant's legally authorized representative).

The investigator, who is a qualified physician, and any designees are responsible for detecting, assessing, documenting, and reporting events that meet the definition of an AE or SAE as well as other reportable safety events. Investigators remain responsible for following up AE, SAEs and other reportable safety events for outcome according to Section 9.3.3.

Adverse events will not be collected for participants during the pre-screening period (for determination of archival tissue status) as long as that participant has not undergone any protocol-specified procedure or intervention. If the participant requires a blood draw, fresh tumor biopsy etc., the participant is first required to provide consent to the main study and AEs will be captured according to guidelines for standard AE reporting.

#### 9.3.1 Time Period and Frequency for Collecting AE, SAE and Other Reportable Safety Event Information

All AEs, SAEs and other reportable safety events that occur after the consent form is signed but before treatment allocation/randomization must be reported by the investigator if the participant is receiving placebo run-in or other run-in treatment, if the event causes the participant to be excluded from the trial, or is the result of a protocol-specified intervention, including but not limited to washout or discontinuation of usual therapy, diet, or a procedure.

From the time of treatment allocation/randomization through 14 days following cessation of treatment, all AEs, SAEs and other reportable safety events must be reported by the investigator.

Additionally, any SAE brought to the attention of an investigator at any time outside of the time period specified in the previous paragraph must be reported immediately to the Sponsor if the event is considered to be drug-related.

Investigators are not obligated to actively seek AE or SAE or other reportable safety events in former study participants. However, if the investigator learns of any SAE, including a death, at any time after a participant has been discharged from the study, and he/she considers the event to be reasonably related to the study treatment or study participation, the investigator must promptly notify the sponsor.

All initial and follow-up AEs, SAEs and other reportable safety events will be recorded and reported to the sponsor or designee within the timeframes as indicated in [Table 8](#).

Table 8 Reporting Time Periods and Timeframes for Adverse Events and Other Reportable Safety Events

Type of Event	Reporting Time Period: Consent to Randomization/Allocation	Reporting Time Period: Randomization/Allocation through Protocol-Specified Follow-up Period	Reporting Time Period: After the Protocol Specified Follow-up Period	Timeframe to Report Event and Follow-up Information to SPONSOR:
Non-Serious Adverse Event (NSAE)	Report if: - due to protocol-specified intervention - causes exclusion - participant is receiving placebo run-in or other run-in treatment	Report all	Not required	Per data entry guidelines
Serious Adverse Event (SAE) including Cancer and Overdose	Report if: - due to protocol-specified intervention - causes exclusion - participant is receiving placebo run-in or other run-in treatment	Report all	Report if: - drug/vaccine related. (Follow ongoing to outcome)	Within 24 hours of learning of event
Pregnancy/Lactation Exposure	Report if: - due to intervention - causes exclusion	Report all	Previously reported – Follow to completion/termination; report outcome	Within 24 hours of learning of event
Event of Clinical Interest (require regulatory reporting)	Report if: - due to intervention - causes exclusion	Report - Potential DILI - Require regulatory reporting	Not required	Within 24 hours of learning of event
Event of Clinical Interest (Do not require regulatory reporting)	Report if: - due to intervention - causes exclusion	Report - non-DILI ECIs and those not requiring regulatory reporting	Not required	Within 5 calendar days of learning of event

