### **9.10.3.1 Safety Follow-up Visit**

The mandatory Safety Follow-up Visit should be conducted approximately 30 days after the last dose of trial treatment or before the initiation of a new anticancer treatment, whichever comes first.

All AEs that occur prior to the Safety Follow-Up Visit should be recorded (up to 30 days following end of treatment). Participants with an AE of Grade >1 will be followed until the resolution of the AE to Grade 0 to 1 or until the beginning of a new anticancer therapy, whichever occurs first. SAEs that occur within 30 days (90 days following administration of pembrolizumab) of the end of treatment or before initiation of a new anticancer treatment should also be followed and recorded.

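### The protocol has no single post-treatment safety window: Section 9.3.1 stops full AE/SAE reporting at 14 days, while Sections 5.1.1 and 9.10.3.1 run to 30 days for AEs and 30 or 90 days for SAEs

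*Combined protocol and SAP*

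**What the plan says.** Three sections of the protocol state how long safety events are collected after treatment.

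- **Section 9.3.1**, the section on collection periods: "From the time of treatment allocation/randomization through 14 days following cessation of treatment, all AEs, SAEs and other reportable safety events must be reported". Outside that period the duty covers "any SAE brought to the attention of an investigator at any time outside of the time period specified in the previous paragraph", and only if the event is considered drug-related. The Synopsis refers to Section 9.3 for follow-up of AEs after treatment, and Appendix 4 refers to Section 9.3.1 for reporting times.
- **Section 5.1.1**: "All participants will be followed for at least 30 days after their last dose of MK-7162 for AE monitoring". For SAEs, "Serious adverse events will be collected for 90 days after discontinuation", or "30 days if the participant initiates new anticancer therapy less than 30 days after study treatment discontinuation", or to the day new therapy starts if that falls between days 30 and 90.
- **Section 9.10.3.1**: "All AEs that occur prior to the Safety Follow-Up Visit should be recorded (up to 30 days following end of treatment"). It also covers "SAEs that occur within 30 days (90 days following administration of pembrolizumab) of the end of treatment" or before new anticancer treatment begins. The safety visit is held at about 30 days, or earlier if new anticancer treatment is about to start.

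Table 8, within Section 9.3.1, requires all events to be reported for the period "Randomization/Allocation through Protocol-Specified Follow-up Period" but does not say how long that period is. After it, non-serious AEs need not be reported.

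The SAP lists AEs among the primary endpoints (Section 10.1) and names DLT incidence as the primary safety endpoint (Section 10.4.2). Section 10.6.2 summarises AEs as counts and frequencies by dose level. Sections 10.5.1 and 10.6.2 give no post-treatment cut-off.

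**The concern.** A site that follows the references to Section 9.3.1 can stop full reporting at day 14. A site that follows Section 5.1.1 or 9.10.3.1 continues to day 30 for AEs and to day 30 or 90 for SAEs. Both would be following the protocol. The by-dose AE and SAE tables would then mix different observation windows, and no rule in the SAP says which events count.

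The safeguard for drug-related SAEs depends on the investigator's judgement at the time. Appendix 4 allows that judgement to change with later information, but an SAE first judged unrelated and never reported is not in the database to be reassessed. Section 7.2.4.2.1 itself says immune-related events may appear several months after the last pembrolizumab dose.

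**Working it through.** The plan gives no figure to reproduce, so the check sets the stated windows side by side. Days are counted from the end of treatment. The SAE rows concern SAEs judged unrelated, since drug-related SAEs are reportable at any time under Section 9.3.1.

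| Situation | 9.3.1 sentence | 5.1.1 | 9.10.3.1 |
|---|---|---|---|
| Non-serious AE, no new therapy | day 14 | at least day 30 | safety visit, at most day 30 |
| SAE, pembrolizumab given, no new therapy | day 14 | day 90 | day 90 |
| SAE, stopped before any pembrolizumab, no new therapy | day 14 | day 90 | day 30 |
| SAE, new therapy on day 10 | day 14 | day 30 | day 10, if its wording means whichever comes first |
| Non-serious AE, new therapy on day 10 | day 14 | at least day 30 | safety visit, on or before day 10 |

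No row agrees across all three sections. Sections 5.1.1 and 9.10.3.1 agree on 90 days for SAEs after pembrolizumab without new therapy, and broadly on 30 days for AEs. They differ in the other situations.

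The anchors are also worded differently: last MK-7162 dose and discontinuation (5.1.1), cessation of treatment (9.3.1), end of treatment (9.10.3.1).

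**Days required elsewhere but not by the 14-day sentence**

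- Non-serious AEs: 30 − 14 = 16 days; 16/30 = 0.53.
- SAEs judged unrelated, 90-day window: 90 − 14 = 76 days; 76/90 = 0.84.
- SAEs judged unrelated, 30-day window (9.10.3.1 without pembrolizumab, or 5.1.1 with new therapy before day 30): 30 − 14 = 16 days.
- SAEs under 5.1.1 with new therapy between days 30 and 90: from 16 to 76 days, depending on the start day.

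**Cover from the safety visit.** Section 2.1 schedules an AE/SAE review at day 30 ± 7, that is, days 23 to 37.

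- Visit on day 30 or later: all 16 AE days (15 to 30) are covered.
- Visit on day 23: 30 − 23 = 7 days (24 to 30) fall after it; 7/16 = 0.44.
- Visit brought forward to day 14 or earlier for new therapy (Sections 9.1.5.2 and 9.10.3.1): all 16 days fall after it.
- SAEs that start after the visit cannot be found at it. The first survival call is due at 12 × 7 = 84 ± 14, that is, days 70 to 98, and Section 9.10.3.2 gives its purpose as survival status.

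**DLTs.** The DLT window is the first 42 days from the first dose. Stopping treatment in Cycle 1 or 2 for treatment-related toxicity is itself a DLT (Section 7.2.2). A participant who stops early for other reasons is generally non-evaluable and replaced (Section 6.5). The post-treatment window therefore hardly touches dose finding.

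**The case against.** The strongest reply is that Section 9.3.1 is more than its 14-day sentence. Table 8 asks for all events through the protocol's follow-up period, and the schedule has a safety visit 30 days after the last dose. On that reading part of Section 9.3.1 already reaches day 30. The reading is possible, but Table 8 does not state it, and it would leave the table in conflict with the sentence in its own section.

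A second reply is that the day counts are conditional. Section 9.10.3.1 records AEs before the visit, with 30 days as a ceiling. Read literally, a visit on day 23 makes its difference from Section 9.3.1 only 23 − 14 = 9 days, and a visit by day 14 makes it nil. If Section 9.10.3.1 stops at new therapy on day 10, Section 9.3.1 is the longer of the two. This stands: the 16 AE days come from Section 5.1.1, or from Section 9.10.3.1 with a visit at day 30 or later, and the 76 SAE days are an upper figure.

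Third, the consequences are modest. The AE summaries are descriptive, and the mandatory visit should pick up most day 15 to 30 AEs when held at day 30. Amendment 02 was written so that the study could close, which limits the value of a prospective change. This also stands and limits the weight of the point, but it does not settle which events belong in the tables.

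**Conclusion.** The concern holds. The current text gives three different post-treatment windows, and nothing in the documents says which governs. At most, 16 of 30 days for non-serious AEs and 76 of 90 days for SAEs judged unrelated are required by other sections but not by the 14-day sentence. The SAE figure assumes a 90-day window with no new anticancer therapy. These are shares of calendar time. Without a post-treatment event rate in the documents, the number of events affected cannot be estimated.

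The weakness lies in the descriptive AE and SAE summaries. It should be fixed, but it does not threaten the dose-finding result.

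**What to change.** Reconcile Sections 5.1.1, 9.3.1 (including Table 8) and 9.10.3.1 so that the following apply throughout:

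- one AE window and one SAE window, including for participants who never received pembrolizumab;
- one time anchor;
- one rule for new anticancer therapy.

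No other section states 14 days, so that sentence needs either alignment or a reason. Define Table 8's follow-up period by the agreed windows, and give the same cut-off for the AE and SAE summaries in Section 10.6.2. Say how events after an early safety visit are captured.

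If SAE collection beyond the 30-day visit is kept, name the contact that will ask about SAEs. The 9-weekly imaging for participants who stop without progression (Section 9.2.4) and the 12-weekly survival calls (Section 9.10.3.2) already exist. As far as the extracted schedule shows, there is no AE/SAE review after the 30-day visit.

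The cost is small: mainly wording, plus an SAE question at an existing contact if the longer window stays.
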